### 4.2.2 Chemotherapy

#### 4.2.2.1

Each cycle of chemotherapy should only be initiated if the absolute neutrophil count is  $\geq 750/\mu\text{L}$  and the platelet count is  $\geq 75,000/\mu\text{L}$ .

#### 4.2.2.2

**Patients < 10 kg will have dosing in mg/kg for all agents.**

#### 4.2.2.3

Filgrastim (G-CSF) should not be given initially and should only be administered prophylactically if there is either a 1 week delay in the administration of chemotherapy because of neutropenia or if the patient requires hospitalization for fever and neutropenia or for sepsis.

### 4.2.3 Concomitant Medications Restrictions

#### 4.2.3.1 Cytochrome P450 interactions

Clinically significant drug interactions have been reported when using irinotecan or vincristine with strong CYP450 3A4 inhibitors and inducers. Selected strong inhibitors of cytochrome P450 3A4 (such as theazole antifungals, fluconazole, voriconazole, itraconazole, ketoconazole and posaconazole) and strong inducers of cytochrome P450 3A4 (e.g. rifampin, phenytoin, phenobarbital, carbamazepine, and St. John's wort) should be avoided while the patient is receiving vincristine, irinotecan or temsirolimus. Aprepitant also interacts with CYP3A4 and should be used with caution with vincristine, irinotecan or temsirolimus. For a list of CYP3A4 inhibitors and inducers see [Appendix V](#).

Fluorouracil may increase the level and effect of CYP2C9 substrates like phenytoin and warfarin. Phenytoin levels and international normalized ratio (INR) should be closely monitored.

The clinical outcome and significance of CYP450 interactions with doxorubicin is less clear. CYP450 3A4 stimulators or inhibitors should be avoided or used with great caution. Additional inducers or inhibitors of CYP450 enzymes can be found at <http://medicine.iupui.edu/clinpharm/ddis>.

4.2.3.2 Anticonvulsant levels (phenytoin, valproic acid and carbamazepine) should be monitored during concurrent use with doxorubicin and cisplatin and phenytoin levels should be monitored in patients receiving cisplatin alone. Patients who are currently receiving enzyme inducing anticonvulsants are not eligible for Stratum 4 (see [Section 3.2.8.2](#)). See [Appendix IV](#) for a list of unacceptable enzyme inducing anticonvulsants.

#### 4.2.4 Supportive Care

For general Supportive Care Guidelines see:

[https://members.childrensoncologygroup.org/prot/reference\\_materials.asp](https://members.childrensoncologygroup.org/prot/reference_materials.asp) under Standard Sections for Protocols.

#### 4.2.5 Radiation Therapy

Since the role of radiation therapy in the treatment of hepatoblastoma is not clearly defined and not typically part of standard care, radiation therapy is **not** permitted on this study.

#### 4.2.6 Treatment Initiation

##### 4.2.6.1

**Please note:** It is recommended that patients who have had > 75% of their liver resected wait at least 2 weeks prior to beginning protocol therapy to allow liver regeneration.

##### 4.2.6.2

**Also note:** Stage I or II patients cannot be enrolled on study or begin protocol treatment until rapid central pathology review is complete.

#### 4.3 Treatment for Very Low-Risk Patients (Stratum 1 – No further treatment)

Patients who have had their tumor completely resected at diagnosis **must** have tumor specimens submitted for rapid central pathology review prior to enrollment onto this study (see [Section 14.0](#) for details). Patients must sign consent giving permission to submit tumor specimens prior to shipment and cannot be enrolled on study until the results of rapid review are known. Patients classified as very low-risk will have their tumor completely resected at diagnosis and then be observed with no further therapy. See [Section 7.6.1](#) for recommended follow-up.

#### 4.4 Treatment for Low-Risk Patients (Stratum 2 - Regimen T)

Patients classified as low-risk **must** have tumor specimens submitted for rapid central pathology review prior to enrollment onto this study (see [Section 14.0](#) for details). Patients must sign consent giving permission to submit tumor specimens prior to shipment and cannot be enrolled on study or start treatment until the results of rapid review are known. Low risk patients will have the tumor completely resected at diagnosis and then receive 2 cycles (each cycle is 21 days) of adjuvant C5V. Patients **must begin protocol therapy within 42 days of definitive surgery to allow for recovery from any surgical complications. However, it is strongly encouraged that patients begin protocol therapy within 28 days of the initial surgical procedure.** Begin each cycle of Regimen T only when the absolute neutrophil count is  $\geq 750/\mu\text{L}$  and the platelet count is  $\geq 75,000/\mu\text{L}$ . **Note: All patients < 10 kg will have dosing in mg/kg.**

##### 4.4.1 CISplatin: IV over 6 hours

100  $\text{mg}/\text{m}^2/\text{dose}$  (3.3  $\text{mg}/\text{kg}/\text{dose}$  for patients < 10 kg) on Day 1.

Recommended hydration and administration guidelines:

Urine specific gravity should be < 1.010 prior to starting CISplatin.

Hours -2 to 0: Prehydrate with 300  $\text{mL}/\text{m}^2$  D5½ NS + MgSO4 8 mEq/L + KCL 20 mEq/L.

Hours 0-6: Infuse CISplatin + mannitol 8000  $\text{mg}/\text{m}^2$  in 750  $\text{mL}/\text{m}^2$  NS @ 125  $\text{mL}/\text{m}^2/\text{hr}$ .

Hours 6-24: D5½NS+ MgSO4 8 mEq/L + KCL 20 mEq/L to run at 125  $\text{mL}/\text{m}^2/\text{hr}$ .

##### 4.4.2 5-Fluorouracil: Slow IV Push over 2-4 minutes

600  $\text{mg}/\text{m}^2/\text{dose}$  (20  $\text{mg}/\text{kg}/\text{dose}$  for patients < 10 kg) on Day 2.

##### 4.4.3 VinCRISTine: IV Push over 1 minute or infusion via minibag as per institutional policy

1.5  $\text{mg}/\text{m}^2/\text{dose}$  (0.05  $\text{mg}/\text{kg}/\text{dose}$  for patients < 10 kg) [Maximum dose: 2 mg] on Days 2, 9 and 16.

Special precautions: FOR INTRAVENOUS USE ONLY.

The container or the syringe containing vinCRISTine must be enclosed in an overwrap bearing the statement “Do not remove covering until moment of injection. For intravenous use only - Fatal if given by other routes.”

Medication errors have occurred due to confusion between vinCRISTine and vinBLASTine. VinCRISTine is available in a liposomal formulation (vinCRISTine sulfate liposomal injection, VSLI, Marqibo®). Use conventional vincristine only; the conventional and liposomal formulations are NOT interchangeable.

See [Section 5.0](#) for Dose Modifications based on Toxicities. The therapy delivery map (TDM) for Regimen T is on the next page (see [Section 4.4.4](#)).

4.4.4 Regimen T – Low-Risk Patients (Stratum 2) Cycles 1 & 2                  Low-risk patients receive 2 adjuvant cycles of C5V. Tumor tissue is strongly encouraged for banking: see ABTR01B1 or other appropriate study for details. This therapy delivery map relates to 2 cycles of C5V therapy. Each cycle lasts 21 days. One cycle is described on this TDM. This TDM is on 1 page. Use a copy of this page once for each cycle (please note cycle number below).
	
_____
 
Patient name or initials                      _____
 
DOB

---	---

Criteria to start each cycle: ANC ≥ 750/μL and the platelet count is ≥ 75,000/μL.

DRUG	ROUTE	DOSAGE	DAYS	IMPORTANT NOTES	OBSERVATIONS
CISplatin (CDDP)	IV over 6 hours	100 mg/m  /dose OR (3.3 mg/kg/dose for < 10 kg)	1	Recommended administration guidelines: Urine S.G. should be < 1.010 prior to starting CDDP. See Section 4.4.1 for pre- and post- hydration & mannitol guidelines.	a. History, physical, ht/wt, BSA, VS ( Start of each cycle & end of therapy ) b. CBC (diff/plt) ( Weekly & end of therapy ) c. Electrolytes, Ca ++ , Mg ++ , PO 4 , creatinine, ALT/AST, bilirubin, total protein/albumin, AFP ( Start of each cycle & end of therapy ) d. Tumor disease evaluation ( End of therapy only ), see Section 7.3 . e. Audiogram ( End of therapy only )  OBTAIN OTHER STUDIES AS REQUIRED FOR GOOD PATIENT CARE
5-Fluorouracil (FU)	Slow IV push over 2-4 minutes	600 mg/m  /dose OR (20 mg/kg/dose for < 10 kg)	2		
VinCRISTine (VCR)	IV push over 1 minute**	1.5 mg/m  /dose OR (0.05 mg/kg/dose for < 10 kg)	2, 9 & 16	Maximum dose: 2 mg ** or infusion via minibag as per institutional policy	

Circle Cycle #: **1 (Weeks 1-3)**    **2 (Weeks 4-6)**                      Ht \_\_\_\_\_ cm                      Wt \_\_\_\_\_ kg                      BSA \_\_\_\_\_ m^2

Date Due	Date Given	Day	CDDP mg	FU mg	VCR mg	Studies	Comments (Include any held doses, or dose modifications)	
			Enter calculated dose above and actual dose administered below					
		1	_____ mg			a, b, c		
		2		_____ mg	_____ mg			
		9			_____ mg	b		
		16			_____ mg	b		
		21	Repeat cycle or (End therapy after Cycle 2)			(a, b ,c, d, e)*	* End of therapy	

See [Section 5.0](#) for Dose Modifications for Toxicities and for general Supportive Care Guidelines see [https://members.childrensoncologygroup.org/prot/reference\\_materials.asp](https://members.childrensoncologygroup.org/prot/reference_materials.asp) under Standard Sections for Protocols.

#### 4.5 Treatment for Intermediate-Risk Patients (Stratum 3 - Regimen F)

**Note: Stratum 3 has been closed to accrual as of 03/12/12.**

All patients with Stage I SCU, Stage II SCU, and Stage III disease will be treated with Regimen F (C5VD). Patients will receive 4 cycles of therapy repeated every 21 days, followed by surgical resection of the tumor or liver transplant (OLT). Patients whose tumors are removed surgically or by OLT after Cycle 4 will receive 2 post-operative cycles of chemotherapy. Patients may have their tumor removed if deemed feasible after 2 cycles of chemotherapy but will then receive 4 cycles of post-operative chemotherapy. **All intermediate-risk patients will receive a total of 6 cycles of chemotherapy.** Patients whose tumors remain unresectable after 4 cycles will be considered off protocol therapy, but will continue to be followed on the AHEP0731 off protocol therapy follow-up CRF. These patients can at the discretion of the primary physician. Additional pre-operative cycles of chemotherapy after Cycle 4 are **NOT** permitted in an attempt to make the tumor resectable or if a liver is not available for transplantation. Patients with progressive disease at any time are off-protocol therapy.

Tumors that are unresectable at diagnosis should be referred to a surgical center with expertise in pediatric liver transplant and “extreme” liver resection as soon as possible. Optimally for planning purposes, this liver transplant consultation should be obtained but at the latest it should be done following the first 2 cycles of neoadjuvant chemotherapy. The consent for the PLUTO registry should be obtained within one month of undergoing liver transplant and is usually obtained by the liver transplant team.

For the purposes of this study, consultation will be defined and may be accomplished in one of two ways:

- The FIRST TIME the patient is seen face to face by the transplant physician/team in the same institution or another institution.
- The FIRST TIME radiographic films and referral material are sent to the transplant physician/team at the same or another institution and are formally reviewed by the transplant physician/team.

The transplant physician/team will communicate the result of this consultation back to the referring physician.

Resection planning is to be completed before completion of the 4th cycle of chemotherapy. Transplant or “extreme” resection is intended to occur within 4 weeks of the completion of the 4th cycle of chemotherapy.

Chemotherapy should resume as soon as possible after surgical resection. In most circumstances this can typically be achieved within 3 weeks following surgery. Patients who do not resume post resection chemotherapy within 42 days of resection will be considered off protocol therapy. Further treatment will be at the discretion of the treating physician.

Patients classified as intermediate-risk will receive 6 cycles of C5VD. Surgical resection of tumor or liver transplant will occur following Cycle 2 (if feasible) or Cycle 4. All patients < 10 kg will have dosing in mg/kg.

##### 4.5.1 CISplatin: IV over 6 hours

100 mg/m^2/dose (3.3 mg/kg/dose for patients < 10 kg) on Day 1.

Recommended hydration and administration guidelines:

Urine specific gravity should be < 1.010 prior to starting cisplatin.

Hours -2 to 0: Prehydrate with 300 mL/m^2 D5 ½ NS + MgSO4 8 mEq/L + KCL 20 mEq/L.

Hours 0-6: Infuse CISplatin + mannitol 8000 mg/m^2 in 750 mL/m^2 NS @ 125 mL/m^2/hr.

Hours 6- 24: D5½NS+ MgSO4 8 mEq/L + KCL 20 mEq/L to run at 125 mL/m^2/hr.

4.5.2 5-Fluorouracil: Slow IV Push over 2-4 minutes

600 mg/m^2/dose (20 mg/kg/dose for patients < 10 kg) on Day 2.

4.5.3 VinCRISTine: IV Push over 1 minute or infusion via minibag as per institutional policy

1.5 mg/m^2/dose (0.05 mg/kg/dose for patients < 10 kg) [Maximum dose: 2 mg] on Days 2, 9 and 16.

4.5.4 DOXOrubicin: IV over 15 minutes

30 mg/m^2/dose (1 mg/kg/dose for patients < 10 kg) on Days 1 and 2.

It is suggested that DOXOrubicin be administered through the tubing of rapidly infusing solution of D5W or 0.9% NaCl and that it is infused into a large vein.

4.5.5 Dexrazoxane: Slow IV Push over 5-15 minutes immediately prior to DOXOrubicin dose

300 mg/m^2/dose (10 mg/kg/dose for patients < 10 kg) on Days 1 and 2 in **Cycles 5 and 6 ONLY**.

The elapsed time from the beginning of the dexrazoxane dose to the end of the DOXOrubicin infusion should be 30 minutes or less.

See [Section 5.0](#) for Dose Modifications based on Toxicities.

#### 4.6 Treatment for High-Risk Patients (Stratum 4) - Regimen H

All high-risk patients will receive 2 cycles of vinCRiStine, irinotecan and temsirolimus (VIT), using a 5 day irinotecan schedule, as “up-front” window therapy on Regimen H. Each cycle lasts 21 days and cycles will start on Weeks 1 and 4. Antibiotics will be given to patients receiving irinotecan who develop chemotherapy-related diarrhea. See “Diarrhea Secondary to Irinotecan” in the Supportive Care Guidelines at: <https://members.childrensoncologygroup.org/prot/reference materials.asp> under Standard Sections for Protocols.

Following 2 cycles of VIT, patients will be evaluated for response (see [Section 10.3](#)). The assessment of response is based on central review of imaging, the alphafetoprotein values and sampling dates. The results of the central review will be returned to the institutional investigator within 3 weeks of submission of the imaging and AFP material. If there is a discrepancy between the assessment by central review and by institutional assessment, the study PI will discuss with the treating physician to resolve the discrepancy. If the investigator selects a post-induction regimen that is *not* indicated by the central review of response, the patient will be considered off protocol therapy as of the start date of consolidation therapy.

Patients who *respond* (demonstrate a complete or partial response) to VIT will then receive a total of 6 cycles of C5VD therapy and 2 more cycles of VIT. Following first 2 cycles of VIT, no further VIT should be given until after surgical resection/liver transplant to avoid potential surgical complications of thrombosis and wound dehiscence. Each cycle lasts 21 days. A total of 10 cycles of chemotherapy (6 cycles of C5VD and 4 cycles of VIT, including the “up-front” window therapy) will be given. VIT is intended to be given during Cycles 7 and 10. However, the order of chemotherapy cycles can be switched at the discretion of the treating oncologists and surgeons to optimize surgical outcomes and minimize complications.

Patients who *do not respond* to VIT will continue with 6 cycles of C5VD repeated every 21 days and receive no further VIT. A total of 8 cycles of chemotherapy (6 cycles of C5VD and 2 cycles of VIT, including the “up-front” window therapy) will be given.

Tumors that are unresectable at diagnosis, even if metastatic disease is present, should be referred to a surgical center with expertise in pediatric liver transplant and “extreme” liver resection should be done as soon as possible. Optimally for planning purposes, this liver transplant consultation should be obtained at diagnosis and no later than the FIRST DAY of the 3rd cycle of C5VD chemotherapy. The consent for the PLUTO registry should be obtained within one month of liver transplant and usually is obtained by the liver transplant team.

For the purposes of this study, consultation will be defined and may be accomplished in one of two ways:

- The FIRST TIME there is documented telephone or email/letter contact and a request for consultation between the treating oncologist and the liver specialty/transplant team.
- The FIRST TIME radiographic films and referral material are sent to the transplant physician/team at the same or another institution and are formally reviewed by the transplant physician/team.

The liver specialty/transplant physician/team will communicate the result of this consultation back to the referring physician.

Resection planning is to be completed before completion of the 4th cycle of C5VD chemotherapy. See Surgical Guidelines in [Section 13.0](#).

Patients will be evaluated after every 2 cycles of C5VD chemotherapy that occur prior to resection. Patients may have their primary tumor removed whenever it is feasible. It is the intent of the treatment that patients should have their tumors removed surgically or by OLT at the latest after Cycle 6 in both responders and

non-responders (ie, after the 4th cycle of C5VD) so that they can receive post-operative cycles of chemotherapy.

Chemotherapy should resume as soon as possible after surgical resection. In most circumstances this can typically be achieved within 3 weeks following surgery. **Patients who do not resume post resection chemotherapy within 42 days of resection will be considered off protocol therapy but not off study.** Further treatment will be at the discretion of the treating physician. Patients will continue to be followed on the AHEP0731 off protocol therapy follow-up CRF.

Regardless of the timing of surgery, patients should receive the total number of cycles as described above.

**Patients whose tumors remain unresectable at the completion of planned therapy will be considered to have experienced an adverse EFS event. No further protocol therapy is planned for such patients. These patients can be treated at the discretion of the primary physician.**

Patients with pulmonary metastases will receive the first 2 cycles of Regimen H chemotherapy described above. If metastases disappear with chemotherapy, no pulmonary surgical intervention will be performed. If metastases are persistent after 4 total cycles of C5VD chemotherapy and the patient is considered a candidate for liver transplant at that time, metastases are to be resected to render the patient free of extrahepatic disease prior to transplant. Transplant may then be undertaken. If the liver tumor can be primarily resected after either 2 or 4 cycles of C5VD chemotherapy without transplant, this should be performed and the final cycles of chemotherapy should be administered. If the metastases are still present, they should then be resected. Pulmonary metastectomy may be performed earlier in the course of therapy if it can be done without resulting in delays in the administration of scheduled chemotherapy.

### Regimen H for Responders

Cycle	1	2	Eval	3	4	5	6	7	8	9	10
Week	1	4			7	10	13	16	19	22	25
Chemotherapy	VIT	VIT		C5VD	C5VD	C5VD	C5VD	VIT	C5VD+ DXRZ*	C5VD+ DXRZ*	VIT

Responders will receive a total of 8 cycles post VIT window.

### Regimen H for Non-Responders

Cycle	1	2	Eval	3	4	5	6	7	8
Week	1	4			7	10	13	16	19
Chemotherapy	VIT	VIT		C5VD	C5VD	C5VD	C5VD	C5VD+ DXRZ*	C5VD+ DXRZ*

Non responders will receive 6 total cycles of C5VD post VIT window.

\*Dexrazoxane administration is not required for patients enrolled in Japan.

**NOTE: For high-risk patients being assessed at the end of Cycle 2, the central review assessment will be returned to the institutional investigator and will indicate the post-induction treatment regimen.**

#### 4.6.1 Criteria to Start Cycle 1 of Regimen H and Subsequent Cycles

##### 4.6.1.1 Criteria to Start Cycle 1 of Regimen H for All High-Risk Patients

Begin Cycle 1 of Regimen H, when ANC  $\geq$  750/ $\mu$ L and the platelet count is  $\geq$  75,000/ $\mu$ L and all the eligibility criteria have been met.

4.6.1.2 Criteria to Start Cycle 2 of Regimen H for **All High-Risk Patients** and Cycles 3-10 of Regimen H for All High-Risk **Responders**

- ANC  $\geq 750/\mu\text{L}$  and the platelet count is  $\geq 75,000/\mu\text{L}$ .
- Total Cholesterol  $\leq 400$  mg/dL OR  $\leq 500$  mg/dL and on lipid lowering medication, AND triglycerides  $\leq 300$  mg/dL OR  $\leq 500$  mg/dL and on lipid lowering medication. If cholesterol or triglyceride parameters are not met based on testing performed in a non-fasting patient, these tests should be repeated after fasting.

4.6.1.3 Criteria to Start Cycles 3-8 of Regimen H for All High-Risk **Non-Responder** Patients

- ANC  $\geq 750/\mu\text{L}$  and the platelet count is  $\geq 75,000/\mu\text{L}$ .

Note: Beyond Cycle 2, the cholesterol and triglyceride parameters to start a cycle of therapy are not applicable for non-responders, as they will not receive any further VIT therapy.

Note: All patients  $< 10$  kg will have dosing in mg/kg

4.6.2 VinCRiStine: IV Push over 1 minute or infusion via minibag as per institutional policy During 'Upfront' Window Therapy for All High-Risk Patients

1.5 mg/m^2/dose (0.05 mg/kg/dose for patients  $< 10$  kg) [Maximum dose: 2 mg] on Days 1 and 8 of Cycles 1 and 2.

During Post 'Upfront' Window Therapy for All High-Risk Responder Patients

1.5 mg/m^2/dose (0.05 mg/kg/dose for patients  $< 10$  kg) [Maximum dose: 2 mg] on Days 2, 9 and 16 of Cycles 3-6, 8-9 **and** Days 1 and 8 of Cycles 7 and 10.

During Post 'Upfront' Window Therapy for All High-Risk Non-responder Patients

1.5 mg/m^2/dose (0.05 mg/kg/dose for patients  $< 10$  kg) [Maximum dose: 2 mg] on Days 2, 9 and 16 of Cycles 3-8.

Special precautions: FOR INTRAVENOUS USE ONLY.

The container or the syringe containing vinCRiStine must be enclosed in an overwrap bearing the statement "Do not remove covering until moment of injection. For intravenous use only - Fatal if given by other routes."

Medication errors have occurred due to confusion between vinCRiStine and vinBLASStine. VinCRiStine is available in a liposomal formulation (vinCRiStine sulfate liposomal injection, VSLI, Marqibo®). Use conventional vincristine only; the conventional and liposomal formulations are NOT interchangeable.

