## 5.6 Temsirolimus

Note: If temsirolimus therapy needs to be discontinued as detailed below, the patient can remain on study and continue with planned therapy while omitting all subsequent doses of temsirolimus.

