### 5.6.2 Dose Modification for Infusional Reactions to Temsirolimus

Therapy modifications for patients who develop infusional reactions to temsirolimus are:

- Grade 1-2: Only dose interruption/discontinuation, but not dose reduction is required for allergic/infusional reactions.
  - If a patient develops a hypersensitivity reaction despite diphenhydramine pretreatment, stop the infusion and wait 30 to 60 minutes (depending upon the reaction severity). At the

physician's discretion, it may be possible to resume treatment by administering an H2 blocker approximately 30 minutes before restarting the infusion. The manufacturer recommends famotidine 0.5 mg/kg IV maximum dose 20 mg, rather than cimetidine, because it lacks reported drug interactions. If famotidine is unavailable, administer ranitidine 1-2 mg/kg IV maximum dose 50 mg. Re-attempt infusion at a slower rate, possibly over 60 minutes.

- If Grade 1-2 infusion reactions recur with subsequent dose, add dexamethasone 0.2 mg/kg (max 10mg) IV or equivalent to premedications above.
- Grade 3: Stop infusion immediately and remove the infusion tube. Administer diphenhydramine hydrochloride 1 mg/kg IV (max 50 mg), dexamethasone 0.2 mg/kg (max 10 mg) IV (or equivalent), bronchodilators for bronchospasms, and other medications as medically indicated. Hospital admission should be considered. Discontinue temsirolimus treatment.
- Grade 4: Stop infusion immediately and remove the infusion tube. Administer diphenhydramine hydrochloride 1 mg/kg (max 50 mg) IV, dexamethasone 0.2 mg/kg (max 10mg) IV (or equivalent), and other anaphylaxis medications as indicated. Epinephrine or bronchodilators should be administered as indicated. Hospital admission for observation may be indicated. Discontinue temsirolimus treatment.

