#### 5.6.3 Dose Modifications for Pneumonitis

For patients who develop pneumonitis (cough, dyspnea, fever), temsirolimus should be held pending investigation. If events are considered at least possibly due to treatment, discontinue temsirolimus therapy. If the treating clinician determines that respiratory symptoms are not related to drug therapy, the patient should be retreated with the same doses of temsirolimus, irinotecan, and vincristine.

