#### 5.6.5 Dose Modifications for Elevated Fasting Cholesterol

The following guidelines should be used for patients who develop elevated fasting cholesterol.

- Grade 2  
Continue temsirolimus; consider treatment with an HMG-CoA reductase inhibitor depending upon recommendations of institutional hyperlipidemia consultants
- Grade 3

An HMG-CoA reductase inhibitor should be started, and dosages adjusted based upon recommendations of institutional hyperlipidemia consultants. It is expected that optimal effects of the lipid lowering medication will be observed 2-4 weeks after its initiation. Treatment with tamsirolimus can continue during this time provided that hypercholesterolemia remains  $\leq$  Grade 3.

- **Grade 4**  
Hold tamsirolimus. An HMG-CoA reductase inhibitor should be started, and dosages should be adjusted based upon recommendations from institutional hyperlipidemia consultants. It is expected that optimal effect of the lipid lowering medication will be observed 2-4 weeks after initiation. Tamsirolimus is to be restarted at the same dose level when recovery to  $\leq$  Grade 3 cholesterol is observed. Upon retreatment with tamsirolimus concurrent with an HMGCoA reductase inhibitor, if Grade 4 elevations recurs, tamsirolimus should be discontinued.

Note: There is a potential drug interaction between mTOR inhibitors and cholesterol lowering agents, particularly atorvastatin. This should be considered when prescribing a cholesterol lowering agent.

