#### 5.6.6 Dose Modifications for Elevated Fasting Triglycerides

The following guidelines should be used for patients who develop elevated fasting triglycerides.

- **Grade 2**  
Continue tamsirolimus; if triglycerides are between 301 and 400 mg/dL consider treatment with an HMG-CoA reductase inhibitor depending upon recommendations of institutional hyperlipidemia consultants. HMG-CoA reductase inhibitor is recommended if triglycerides are between 401 and 500.
- **Grade 3-4**  
Hold tamsirolimus until recovery to  $\leq$  Grade 2. An HMG-CoA reductase inhibitor should be started, and dosages should be adjusted based upon recommendations from institutional hyperlipidemia consultants. Upon retreatment at the same dose level, if Grade 3 or 4 toxicity recurs, lipid lowering medication should be adjusted in consultation with institutional hyperlipidemia consultants. Tamsirolimus should be held until recovery to  $\leq$  Grade 2. Upon retreatment with tamsirolimus concurrent with an HMGCoA reductase inhibitor, if Grade 3 or 4 elevations recur, tamsirolimus should be discontinued.

Note: There is a potential drug interaction between mTOR inhibitors and cholesterol lowering agents, particularly atorvastatin. This should be considered when prescribing a cholesterol lowering agent.

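### Section 4.6.1.2 keeps the lipid start limits on a responder who has permanently stopped temsirolimus, although Section 4.6.1.3 waives them for patients due no further VIT

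*Combined protocol and SAP*

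**What the plan says.** Section 4.6.1.2 covers Cycle 2 for every high-risk patient and Cycles 3-10 for responders. It requires ANC >=750/uL, platelets >=75,000/uL, total cholesterol <=400 mg/dL (<=500 on lipid-lowering medication) and triglycerides <=300 mg/dL (<=500 on such medication). A non-fasting failure is repeated fasting. The responder delivery maps, including 4.6.10.a and 4.6.10.c for the C5VD cycles, refer to this section for their start criteria.

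Section 4.6.1.3 starts non-responder Cycles 3-8 on ANC and platelets alone. Its note gives the reason, for cycles after the window: "cholesterol and triglyceride parameters to start a cycle of therapy are not applicable for non-responders, as they will not receive any further VIT therapy".

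Section 5.6 opens with the rule for a patient whose temsirolimus must be stopped: "the patient can remain on study and continue with planned therapy while omitting all subsequent doses of temsirolimus". It does not mention cycle start criteria, and 4.6.1.2 does not mention patients who are off the drug.

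For Grade 3-4 triglycerides, Section 5.6.6 acts on temsirolimus only: "Hold tamsirolimus until recovery to" Grade 2 or lower.

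**The concern.** The protocol gives its own reason for waiving the lipid limits: no further VIT is due. That reason applies equally to a responder who has permanently stopped temsirolimus, but the waiver depends on response status and so misses this patient. Section 5.6 intends treatment to go on; 4.6.1.2, followed as written, can stop it. What would be held is C5VD, which contains cisplatin and doxorubicin, the two agents that Section 2.1 ranks as most active in this disease. The rest of a responder's treatment after the window is built around it.

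**Working it through.** No design figure is involved, so there is no stated number to reproduce. The check sets the sections side by side and counts cycles.

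**1. What the limits guard against.** In the toxicity tables of Section 6, cisplatin, 5-fluorouracil, vincristine, doxorubicin and irinotecan list no cholesterol or triglyceride effect. Temsirolimus does (6.1). Dexrazoxane lists occasional transient triglyceride rises (6.3), but non-responders receive it in Cycles 7-8 without a lipid gate. The gate therefore belongs to temsirolimus.

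**2. Cycles gated.** Responders have 10 - 2 = 8 cycles after the window. C5VD is Cycles 3, 4, 5, 6, 8 and 9 (6 cycles); VIT is Cycles 7 and 10 (2 cycles). All 8 carry the lipid condition. Of the 6 non-responder cycles after the window, none does.

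**3. How a responder comes to be off the drug.**
- Grade 3 infusion reaction (5.6.2): "Hospital admission should be considered. Discontinue temsirolimus treatment". Grade 4 is handled the same way. Pneumonitis (5.6.3): "If events are considered at least possibly due to treatment, discontinue temsirolimus therapy". Either stops the drug at once. If this happens in Cycle 2, Cycles 3-10 remain: 8 gated, 0 with temsirolimus.
- Triglycerides (5.6.6), read in sequence: a first Grade 3-4 episode holds the drug. Then "Upon retreatment at the same dose level, if Grade 3 or 4 toxicity recurs, lipid lowering medication should be adjusted". Then "Upon retreatment with tamsirolimus concurrent with an HMGCoA reductase inhibitor, if Grade 3 or 4 elevations recur, tamsirolimus should be discontinued". That is three episodes. With doses in Cycles 1, 2 and 7 and lipids tested on Day 1, they appear at Day 1 of Cycles 2, 3 and 8. Cycles 8, 9 and 10 remain: 3 gated, of which 2 are C5VD.
- Cholesterol (5.6.5): a second Grade 4 episode, on retreatment with a statin, stops the drug. On Day 1 tests, the two episodes can fall at Cycles 2 and 3, again leaving 8 gated cycles.

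**4. Which values hold a cycle.** Triglycerides of 301-500 mg/dL or cholesterol of 401-500 mg/dL pass once lipid-lowering medication is started, and 4.6.1.2 sets no minimum time on it. Only fasting values above 500 mg/dL truly hold the cycle.

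**5. Length of a hold.** The protocol gives no figure. The nearest guide is 5.6.5, for cholesterol: "optimal effect of the lipid lowering medication will be observed 2-4 weeks after initiation", that is 14-28 days, or up to 28/21 = 1.3 cycle lengths. This is time to best effect, not time to fall below 500 mg/dL.

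**6. Patients in reach.** Closure on July 20, 2018 to the version date of November 7, 2018 is 110 days. The responder plan lasts at least 10 x 21 = 210 days. Anyone starting in the last 210 - 110 = 100 days before closure could still be on treatment. Assuming accrual at the planned 16 per year up to closure, that is 16 x 100/365 = 4.4 patients, or 2.0 to 2.9 responders at response rates of 45% to 65%. A surgical gap lengthens the plan and raises this somewhat. It could also be none: 43 patients at 16 per year is 2.7 years, so stratum 4 may have filled earlier. The share who stop temsirolimus permanently is not given.

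**7. Responders still due temsirolimus (optional change only).** Days from each C5VD Day 1 to the next VIT:

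| Cycle | 3 | 4 | 5 | 6 | 8 | 9 |
|---|---|---|---|---|---|---|
| Days | 84 | 63 | 42 | 21 | 42 | 21 |

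Against 14-28 days for medication, four of the six gates leave enough time to treat lipids without holding C5VD. At Cycles 6 and 9 the next VIT might start 28 - 21 = 7 days late. After Cycle 6 this is a ceiling, because resection or transplant is intended by then and lengthens the interval.

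**The case against.** A reader might infer that lipid-gating any C5VD cycle is an error, and that 6 of the 8 cycles are wrongly gated for every responder. The documents do not support that. The protocol divides patients by whether more VIT is coming, and most responders have it coming, in an order that Section 4.6 allows to be switched. One rule for all responder cycles is simple and defensible. Section 5.6.6 governs temsirolimus dosing and 4.6.1.2 governs cycle start, so one being stricter is not a contradiction. Nor can it be said that no drug in the held cycles raises lipids: outside Japan, Cycles 8 and 9 include dexrazoxane.

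The count of 8 gated cycles is also a count of laboratory checks, not of delays. Infusion reactions and pneumonitis are not lipid events, entry required both lipids <=300 mg/dL, and Section 6.1 gives half-lives of 17.3 hours (temsirolimus) and 54.6 hours (sirolimus). Such a patient would rarely exceed 500 mg/dL later. A patient who stopped because of lipids is the likelier case, and on the triglyceride route only Cycles 8-10 are left.

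All of this stands, and it limits the point to patients permanently off the drug. It does not remove it. Nothing in 4.6.1.2, 5.6 or the maps gives them a waiver, and dexrazoxane cannot be the reason, since non-responders receive it ungated.

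**Conclusion.** The gap is real and minor. For a responder permanently off temsirolimus, 4.6.1.2 retains a start condition whose stated purpose has gone, and 5.6 does not override it. A literal reading holds C5VD at fasting triglycerides or cholesterol above 500 mg/dL. Between 3 and 8 cycles are exposed, depending on why and when the drug stopped. No delayed cycle can be shown from the documents, and the number of patients is probably very small and may be zero. That estimate rests on the planned accrual rate, 21-day cycles and Day 1 lipid tests.

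A reader might also infer a bias in the stratum 4 response rate. There is none from these gates: response is read at the end of Cycle 2, before Cycles 3-10 begin. The effect is on treatment delivery only.

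**What to change.** Add to Section 4.6.1.2 that the cholesterol and triglyceride criteria do not apply to patients who have permanently discontinued temsirolimus, who start cycles on ANC >=750/uL and platelets >=75,000/uL as in 4.6.1.3. Maps 4.6.10.a and 4.6.10.c already point to 4.6.1.2 and need no change. Because 4.6.1.2 also covers Cycle 2, the sentence would reach a patient who stopped the drug in Cycle 1. The cost is one sentence in an amendment, with no new tests.

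Optionally, for responders still due temsirolimus, limit the lipid gate to cycles in which temsirolimus is planned, wherever they fall, so that C5VD is not held when 5.6.6 would hold only temsirolimus. Lipids would still be measured each cycle under Section 7.5 and treated as needed. The cost is somewhat looser lipid control before the next VIT, mainly at Cycles 6 and 9. Leaving this part as it is would be reasonable.
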